Protocol Title: Acceptability of HPV self-sampling tools for cervical cancer prevention in Jamaican women: A theory-based approach to culturally-tailored message design.

Version: 1A

Version Date: April 27, 2018

NCT Number: NCT03613493

1) Protocol Title

Acceptability of HPV self-sampling tools for cervical cancer prevention in Jamaican women: A theory-based approach to culturally-tailored message design.

2) IRB Review History*

N/A

3) Objectives*

The purpose of the proposed study is to increase HPV screening behaviors in Jamaican women by examining the acceptability of HPV DNA self-sampling tools, and determine the most culturally appropriate and effective message design for promoting such a tool in this context.

Specific Aim: Evaluate culturally-tailored HPV DNA self-sampling toolkit.

H1: Women who receive culturally tailored messaging will exhibit improved screening, screening-relevant knowledge, attitudes, and perceived-efficacy.

4) Background*

Low screening coverage is related to health system barriers, as well as women's attitudes and knowledge about cervical cancer screening. In a study conducted by the Ministry of Health and Environment of Jamaica in 2008, lack of uptake was found to be influenced to a significant degree by fears and misconceptions on the part of Jamaican women, including ideas that the human papillomavirus (HPV) test causes damage to the cervix. In addition, other factors impeding women in Jamaica include concerns about privacy, belief that the procedure was embarrassing, ignorance about where to get a pap test, and lack of sufficient information, fear of pain, fear of cervical cancer diagnosis, and lack of sufficient time with their doctors.

The US Food and Drug Administration has designated HPV screening as a best practice in identifying risk of cervical cancer, over and above pap test screening, because of its high efficacy, affordability, and convenience, since it can be adapted for various settings. The HPV self-sampling tool has been shown to address issues such as privacy, and studies have shown that women feel more comfortable with this option and expressed willingness to recommend the tool to others. This adaptability has become a driving force in advocates support for the tool in hard-to-reach and poor areas. HPV self-sampling has been tested in many contexts, including resource-limited countries, and has been found to be efficacious and cost-effective. With this now fairly well-established in the literature, research questions have now focused on the best strategies for diffusion of the tools. It has been suggested that Community Health Workers (CHWs), coupled with Community-based Participatory Research (CBPR) methods are the ideal vehicle to ensure optimal uptake in community-settings. On the other hand, other studies have proposed that a mailed approach is preferred.

This current proposal aims to determine how culturally appropriate messaging within one context (Jamaica), alongside an innovation (self-sampling HPV test), might increase uptake of screening behaviors.

5) Inclusion and Exclusion Criteria*

Rationale for inclusion/exclusion criteria: This study will involve the collection of data from Jamaican women. Eligible participants will be accepted to the study on a first-come- first-serve basis. A prescreening survey in person or over the phone (see Appendix A), as well as the data from the baseline survey (see Appendix B), which will include a demographic section which will include self-reporting of age etc. (listed below) which will be an additional check for confirming eligibility for the study.

Inclusion criteria: Jamaican women, aged 30 to 65.

Exclusion criteria: women who report having had a hysterectomy, have had a history of cervical cancer, Women who are currently up-to-date on cervical cancer screening (have had a Pap in the last 3 years or have had a Pap smear/HPV co-test within the past 5 years), adults unable to consent, children, pregnant women and prisoners.

6) Number of Subjects*

Total expected: approximately 360 participants, (350 for the intervention; 10 interviews)

7) Study-Wide Recruitment Methods*

Jamaican women will be recruited for participation in two different phases of this research project. Efforts will be made to include women from rural areas, urban areas, and varying socio economic and cultural backgrounds. Recruitment will occur in three identified low-screening regions in Jamaica (using national statistical data on screening rates per parish in Jamaica), and enrolment will take place through local community organizations as well as at community events such as health fairs.

8) Study Timelines*

An individual subject in the research is expected to participate up to maximum of 4 months. Enrolling study subjects is expected to not exceed one month prior to the actual study date. The estimated date for the investigators to complete this study is September 30, 2018. The primary data analysis will be completed by October 31, 2018. Other studies that have utilized community and government partners have been successful at recruiting a similar number of participants over a short time. For example (Barrett & Huffman, 2011) collected their entire dataset in 3 weeks in October 2007 (276 Jamaican adolescents). Another example is (Lewis-Bell et al., 2013), a cross-sectional study that

took place in April–July 2010 with 852 sexually-active Jamaican women, 16–49 years of age.

9) Study Endpoints*

The primary study endpoints are:

- Development of messages and design of HPV self-sampling tool kit.

Based on formative results from interviews (see Appendix C for interview script), messages will be designed that are culturally appropriate and tailored for any audience segments which emerge from the data. Feedback will be used to design a culturally adapted HPV DNA self- sampling toolkit for this context.

- Evaluation of culturally-tailored HPV DNA self-sampling toolkit.

Enrolled participants will complete a pre-test/baseline questionnaire which will be based on the theoretical constructs identified, and which will also be assessed in the posttest. The intervention will be considered a success when: 1) the majority of women targeted opt to return their sample, as instructed on the toolkit, for testing and, 2) upon evaluation (posttest - See Appendix C), women report higher levels of, knowledge, self-efficacy and response efficacy or positive changes in attitudes toward screening than at baseline.

10) Procedures Involved*

Interviews

Determination of eligibility: The Jamaica Cancer Society (JCS) will provide support to select 10 individuals for interviews using their database (purposive sampling) from at least 2 of their clinic-based locations. Eligibility will be determined according to the inclusion/exclusion criteria outlined as well as during the pre-screening process (Appendix A).

Procedure: Participants who express an interest will be screened, consented and given the baseline survey to complete, by a local study coordinator or the Co-I. They will then be given the self-sampler tool to use at home. A date, time and location to return the tool and participate in the interview process (within the same week) will be determined with the participant at the time of consent. Participants will be reminded of this by at least one telephone call up to the day of the interview. After the interviews, participants will also complete the baseline survey. The interviews will function as a piloting of the baseline and posttest questionnaires as well as a pretest of the collection of self-samples (described below), since participants will actually use and return a self-sampling tool before conducting the interview. The location for the interviews will be at the JCS. The participants will receive their hpv test results within 6 weeks of the interviews.

Narrative interviews: For the purpose of social science research, narrative interviews are unstructured and in-depth and ask participants to reconstruct a particular event that is important to them and their social context, in the format of a story, for an interviewer (Rohleder & Gibson, 2005). The method seeks to understand how people's narration of stories also demonstrates people's ways of thinking or their "unconscious logic" (Hollway, 2001, p. 15). Moving beyond the traditional question-response format, narrative interviewers have a diminished role. Instead the interview relies on certain expected schema in storytelling to elicit the sought-after rich data. This schema dictates that the respondent will naturally share the most pertinent information, provide sufficient detail, and include a structure that includes a beginning, middle and end of the main situation or occurrence being described. After the participants are asked to tell their story, the interview may not interrupt at any point to ask for further explanations or to express any opinions; the interviewee may only ask what happened next (Rohleder & Gibson, 2005). See Appendix C for interview script.

Tailoring the self-sampler messages (package and instructions): The participant responses will provide insight into local women's' perceptions, language, experience using the tool, which will further aid message design. The interviews will provide insight on the participants experience using the toolkit and how this is expressed linguistically. For example, in their own words how did they use the self-sampler tool. This will inform further the language and wording choices for the culturally-tailored condition.

Collection of Self-Samples:

Determination of eligibility: Participants in the full intervention (350 women) will be screened for eligibility by the CO-I or a local study coordinator. The Co-I/local study coordinator will administer a brief screening questionnaire prior to obtaining informed consent (Appendix A). The screening questionnaire will cover the inclusion/exclusion criteria listed above. For women who screen potentially eligible, the CO-I/local study coordinator will further describe the study. Eligible potential participants will be told that we are conducting a research study to understand how new innovations like an at-home HPV self-sampling tool would be accepted by you and in your community. The study will involve completion of a baseline survey (Appendix B) about their sexual and reproductive practices and cervical self-sampling.

In our research, we plan to use a self-sampling device developed by Preventive Oncology International (POI) and the National Institutes of Health (NIH). The POI/NIH self-sampler is considered a non-significant risk device and has been approved for research conducted by NIH faculty throughout the United States and in various international settings. This device is manufactured by Puritan Medical Products, and is thought to reflect an improvement over other self-samplers, given a larger Collection Swab tip, which enables a woman to collect cells from more of

the cervix's total surface area with less effort. The POI/NIH self-sampler is a 20 cm in diameter, which is similar to a regular-sized tampon. This sampler is easy to use. A woman inserts the device into her vagina until she feels slight resistance. The participant then holds the paddle end of the Collection Swab and rotates it five times. She then withdraws the Collection Swab. Once the Collection Swab is fully removed from the vagina, the participant places the Collection Swab into liquid cell preservative and rotates it five times. The participant can then dispose of the swab in a household trash can and secure the vial lid. The participant should return the vial by mail (she will be provided a pre-addressed, stamped envelope) or in person to a specified return location. The CO-I/local study coordinator will be responsible for storing and shipment of the samples to the SCCC for testing.

Participants will receive the HPV self-sampler at the time they complete the baseline survey with the Co-I/local study coordinator. The HPV self-sampler kit will include the collection swab and the vial for collecting and storing the specimen, and an instructional sheet that visually depicts the steps for self-sampling. 115 women will receive a culturally-targeted, fear appeal message for the HPV self-sampler kit; 115 women will receive only a fear appeal message, not targeted for the Jamaican populace; and 115 women will receive only the self-sampler tool with no message appeal (plain packaging). (Appendix G & J). The Co-I/local study coordinator will offer the HPV self-sampler accompanied by an instruction sheet on how to use the self-sampler. At this point participants will receive some sensitization on the topic, which will include: 1) health education on the importance of cervical cancer screening using a short intervention/educational script (Appendix H) and 2) motivation to encourage women to have screening using the HPV self-sampler. Women will also be informed of the following: 1) HPV infection usually is not detectable or harmful; 2) nearly everyone who has had sexual intercourse has been exposed to HPV and infection is very common; 3) a positive HPV test result does not indicate the presence of cancer and that not all women who test positive for an HPV infection will not develop advanced cancer. It will also be stressed to women that if they have not seen a doctor recently they will still need to see a provider to address other health issues, which may include a gynecologic exam. They will also be advised that if HPV obtained through self-sampling is positive, they will need follow-up medical care at clinical sites (a list of possible sites will be provided). and to package and return it by mail or to the address provided. A brief survey on intentions will then be administered (Appendix K). Participants will be asked to use the tool at home by following the instructions, The local study coordinator will follow up with participants who do not return the kit within 1 week via SMS messaging. All participants will receive the following message: "Please remember to return your HPV self-sampler kit to X location during the following times: X Y, and Z. Please ignore this message if you have already returned the kit. Thank you."

Posttest Interview: All participants will be asked to complete a posttest survey which may be administered by phone or in person, if convenient (Appendix D) upon return of the self-sampler kit.

Compensation: All participants will be provided a one-time small incentive of approximately \$21USD (\$2,500 Jamaican dollars) immediately upon completion of the narrative interviews (for the interview participants), and upon completion of the posttest interviews (for the message design experiment participants).

Report of HPV Lab Results: The Co-I will receive test results from lab and provide information to the local study coordinator. The Co-I/local study coordinator will call participants within 4-6 weeks to notify them of their test results when they are received.

Participants who test negative will be encouraged to follow-up with their doctor and rescreen in 36 months, based on the US Preventive Services Task Force (USPSTF) guidelines. Participants whose test results indicate insufficient sample (insufficient cellular quantity for analysis) would be asked if they had a hysterectomy. If no, the participant will have the option of providing a second sample if they are located within reasonable distance from a local project partner, and an appointment will be scheduled by Co-I/local study coordinator to either deliver the kit or for the participant to pick up. Participants who test positive for HPV will be navigated to appropriate follow-up care with our community partners and/or The Ministry of Health Jamaica within 30 days of receiving the result. The Co-I will work with Ministry of Health staff to ensure that women with abnormal findings receive timely follow up. The Co-I/local study coordinator will follow up with participants who do not return the kit within 30 days.

For individuals who screen eligible but declined consent/enrollment, the brief demographic information collected during the eligibility screen (age, ethnicity) will be kept without any identifiable information so that we may compare responders versus non-responders. For individuals who choose to participate in the study, the CO-I/local study coordinator will obtain consent (see Appendix F), complete the baseline survey (Appendix B) and give the self-sampling tool (or schedule a time to do so at a time or location convenient for the participant).

11) Data and Specimen Banking*

The local study coordinator will transport any samples from the field then batch-shipped to UM Sylvester Comprehensive Cancer Center (SCCC) via DHL. The study coordinator will be in charge of the logistics related to receiving the samples from the field, storing them and shipping them (this corresponds with other projects that have successfully used these methods in the collection of HPV dna samples (see [Lewis-Bell et al. 2013](#)). We will ship the self-sampled specimens to the SCCC for high-risk HPV detection and HPV viral genotyping. Cervical specimens will be labeled with a number that matches the number assigned to the participant during the study intake. The specimens will be

processed and results will be reported back to Co-I within 2 weeks, who will obtain signature from [name]. He will sign and date lab result sheet. Copies of results will be filed and kept in locked cabinet and uploaded to REDCap. Copies of analysis will be given to the study team who will be filed and kept in locked cabinet and uploaded to RedCap.

12) Data Management*

All study data will be captured by REDCap (<http://project-redcap.org/>), and Velos (velos.med.miami.edu), which provides both secure data capture for clinical research studies. The REDCap (Research Electronic Data Capture) system (project-redcap.org/) is a web-based clinical research management application that is designed specifically for investigators and their research teams. It supports processes for patient recruitment, patient scheduling, budgeting, invoicing, and milestone management, data safety monitoring, adverse event reporting, system integration, data collection and study execution. Data safety checks, redundancy, and skip patterns can all be easily programmed. A major strength for our proposal is that REDCap allows all study related information to be centralized yet be accessed through the internet from anywhere through encrypted and password protected access granted only to authorized personnel as designated by the study PIs. It is easy to use, reliable, fully HIPAA compliant and completely secure. A major advantage of using this system is that UM provides this important resource to UM and associates (such as non-UM community research partners) at no cost. This includes technical support and effort of REDCap team staff who assists investigators in uploading all their surveys and questionnaires into REDCap. In this study, all of the data collected at the time of interview or site visit by the Co-I/local study coordinator will be uploaded in real time into REDCap system using iPads. However, the Co-I will also have paper versions of the instrument for the anticipated but hopefully rare occasions when technological glitches occur. In these cases the Co-I/local study coordinator would input the data at a later time.

All data will be inspected for quality assurance prior to analysis. Prior to performing statistical analysis on quantitative data, the data will be checked, screened and verified. Data checking is critical to ensure the integrity of the database. Range checks will be routinely performed, and random items from the raw data will be checked against the entered data so that mistakes can be identified. the sampling strategy for our study may be described as purposive and snowball sampling. Women will not be not randomly selected as the study was intended to capture a community-based population that meets specific selection criteria. Data will be analyzed from interviews using the constant comparison method (Corbin & Strauss, 2008). For the message design experiment, a paired t-test will be conducted to determine the difference between pre and posttests in screening behavior after exposure to the self-sampling tool; mediation analyses will be conducted to determine if change in screening knowledge, attitudes and perceived-efficacy mediated changes in screening outcomes. Mediation analyses

will be performed using ordinary least squares regression, using techniques recommended for within-subject designs (Judd, Kenny, & McClelland, 2001).

To maintain participant confidentiality, study specific ID codes are used in all study tracking and analyses. Only the Co-I/local study coordinator will have access to the files linking participants with study ID numbers.

13) Provisions to Monitor the Data to Ensure the Safety of Subjects*

All study data collected will be uploaded into the REDCap system. As previously stated, the Co-I and local coordinator have access to this system to enter participant data using an iPad or paper-based methods during interviews and site visits, and in real time during the evaluation phone call.

Furthermore, quality and completeness of data entry will be systematically checked by a data manager at regular intervals for the duration of the study. Only the Co-I has access to the raw data files entered by the Co-I/local study coordinator. De-identified data files that have been cleaned and appropriately grouped and categorized will be made available to study personnel requesting such data.

Additionally, all study staff and the PI will meet monthly to review study progress, as well as discuss any adverse events and feedback from participants regarding study procedures. Finally, study data is reviewed on a regular basis to ensure proper entry and storage procedures.

14) Withdrawal of Subjects*

Any participant may choose to withdraw from the study at any time. If a participant chooses to withdraw, their data will be destroyed, and their reason for withdrawal recorded. Participants may withdraw by contacting the Co-I/local study coordinator.

15) Risks to Subjects*

Participants in the study will be asked a series of questions about their beliefs, attitudes, and practices related to their sexual and reproductive history and health seeking behaviors. There is no risk of physical injury from answering these questions. However, the topic is sensitive in nature, and participants may feel uncomfortable answering some questions about their personal feelings and beliefs, and about the details of their behavior. Participants may also find themselves opening up about health issues and concerns that they have previously kept private, which may cause some emotional discomfort.

Regarding the cervical self-sampling device, the two most common prior problems of self-sampling were: 1) placing the sampler in an incorrect opening (e.g., the anus); and 2) Injury to the vagina or cervix due to aggressive sampling.

Also, a participant may experience cervical bleeding and inflammation from excessive pressure applied during the rotation of the device. If a participant experiences continuous and heavy bleeding, they are advised to stop using the device and contact the study team immediately. However, both of these hazards are unlikely to occur with the current device. In trials with more than 20,000 women when either problem has occurred, they did not cause serious injury. Rather, they resulted in minimal patient discomfort. Thus, it is considered a non-significant risk device.

There are psychological risks associated with receiving an abnormal test result from self-sampling. Participants may interpret an abnormal result as a diagnosis of cancer rather than an infection with HPV. The participant may feel hopeless in response to an abnormal result, believing that there is nothing that can help. As a member of an underserved group she may feel that adequate health services are not available or accessible to her. She may also feel guilty that she has done something wrong or someone has wished ill health upon her. She may feel embarrassed to tell her friends, family, and other ones, fearful of how they may judge her and reflect upon her diagnosis.

If the participant decides that they do not wish to participate in the study after it has started, they will be advised to tell the Co-I or local study coordinator. They will be advised that there is no penalty imposed if they decide to end their participation early and/or refuse to answer any question.

Adverse Experience Reporting: If any participant who chooses to use the HPV self-sampler indicates to the local study coordinator or Co-I that a discomfort is persistent or something else has occurred, the Co-I should contact directly the Principal Investigator and oversight committee of the study. Participants who experience any adverse effect or study-related injury will be navigated to appropriate follow-up care with our community partners and/or The Ministry of Health Jamaica immediately for follow-up care.

16) Potential Benefits to Subjects*

A potential benefit for all participants is the opportunity to be screened. There are no other direct benefits to participants from taking part in the study.

17) Vulnerable Populations*

This research does not involve individuals who are vulnerable to coercion or undue influence or vulnerable populations.

18) Multi-Site Research*

N/A

19) Community-Based Participatory Research*

This project shares some elements of community-engaged research. Firstly, the community will be involved in the conduct of the study as participants, to improve the utilization of local knowledge in the development of an effective intervention or program at a national level. Secondly, we will collaborate with local institutions to plan the research project and for assistance in the recruitment of participants.

20) Sharing of Results with Subjects*

After participants return their tests by mail (or do not), results will be analyzed within 6 weeks and sent to the local study coordinator, who will call participants to give the results of their tests. Those who do not return their kit will also be called. All women who test positive for high-risk HPV will receive information on follow-up procedures, which will be available at local health facilities.

In addition to disseminating our findings through journals, conferences, and other standard academic channels, our community partners will oversee the dissemination of research findings within our target communities.

21) Setting

The Co-I/local study investigator will identify and recruit potential subjects at various community venues or NGOs (such as the Jamaica Cancer Society) that they deem appropriate and at which women tend to congregate. These may include, but are not limited to: churches, health clinics, markets health fairs and other events. Parishes that have been identified as low-screening areas will be targeted. Additionally, participants will be asked to refer others to the study by providing the names and phone numbers of up to three additional women.

Interviews will be conducted at a location convenient for the participant or in a private location to be identified (e.g. Jamaica Cancer Society office).

22) Resources Available

- [name] [name] Candidate, Co- Investigator, School of Communication, University of Miami. [name] will be responsible for all aspects of the research implementation, including: data collection and/or management, study coordination, data analysis and/or statistics, participant screening/recruitment, social and/or behavioral assessment, interviews.

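### Success criterion 1 names no arm and no comparator, so it can be met while the tailored arm returns the fewest kits

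*Combined protocol and SAP*

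**What the plan says.** All references are to the combined protocol and SAP.

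- **Section 3 (H1)** is about one message type: "Women who receive culturally tailored messaging will exhibit improved screening".
- **Section 9** lists as a primary endpoint "Evaluation of culturally-tailored HPV DNA self-sampling toolkit" and gives a two-part success rule beneath it. Part 1 is that "the majority of women targeted opt to return their sample, as instructed on the toolkit, for testing". Part 2, joined to it by *and*, is that "women report higher levels of, knowledge, self-efficacy and response efficacy or positive changes in attitudes toward screening than at baseline". Neither part names an arm or a comparator, and part 1 has no stated denominator or interval.
- **Section 10** describes three groups. For the first, "115 women will receive a culturally-targeted, fear appeal message for the HPV self-sampler kit". A second group of the same size gets an untailored fear appeal, and a third, also of 115, gets plain packaging with no message.
- **Section 12** holds the quantitative analysis plan: a paired t-test of screening behavior before and after, and mediation analyses for within-subject designs. It contains no comparison of return rates between groups.
- **Section 14** states that the data of a woman who withdraws are destroyed.

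**The concern.** H1 asks whether the tailored message improves screening. The success rule asks only whether more than half of some group of women sent a sample back. A high return rate could come from the kit itself, the education script or the SMS reminder, and Section 10 gives these to every group. The rule cannot separate them from the tailoring.

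The stake is the headline conclusion. Followed as written, the trial can report the tailored toolkit as a success when women given that toolkit were the least likely to return a sample. No other planned analysis would show the contradiction.

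**Working it through.** **Inputs from the documents.** Three groups of 115 (Section 10), so 3 × 115 = 345. Section 6 gives 350 for the intervention phase without a derivation, so there is no planned figure to reproduce. The documents give no expected return rate, and all return rates below are illustrative assumptions.

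**Bare majority.** The smallest count above n/2 is floor(n/2) + 1: 173 for n = 345, 176 for n = 350 and 58 for n = 115.

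**Reading A: all three groups pooled.**
- Observed counts: tailored 46/115 = 40.0%; each other group 64/115 = 55.7%.
- Total: 46 + 64 + 64 = 174, and 174/345 = 50.4%. Since 174 ≥ 173, criterion 1 is met.
- Tailored minus either other group: (46 − 64)/115 = −15.7 percentage points. Standard error = √(0.400 × 0.600/115 + 0.557 × 0.443/115) = 0.065. The approximate 95% CI is −15.7 ± 1.96 × 6.5, or −28.4 to −2.9 points. Data that meet the criterion can therefore point clearly against tailoring.
- With 350 as denominator, 46 + 65 + 65 = 176 also passes, so the result does not depend on the 345/350 difference.
- As probabilities (exact sum of three independent binomials, at least 173 returns): true rates of 40/60/60% for tailored/untargeted/plain meet the criterion 89.7% of the time, and 45/55/60% meet it 89.4% of the time.

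**Reading B: tailored group only.**
- 46/115 is below 58, so the Reading A example fails here.
- 69/115 = 60.0% passes. If each other group returns 86/115 = 74.8%, the tailored group is lower by 17/115 = 14.8 points and criterion 1 is still met.
- P(X ≥ 58 | 115, p) is 85.9% at p = 0.55 and 98.5% at p = 0.60, whatever the other groups do.

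**Does anything else in the plan catch this?**
- Criterion 2 must also hold, but it is a change from baseline with no comparison group. Knowledge and efficacy can rise in every group after the shared education script.
- The paired t-test and the within-subject mediation in Section 12 do not compare groups.

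**Would a confidence bound repair it?** An exact lower 95% limit above 50% needs 69/115 in the tailored group.

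| True tailored rate | Chance of ≥ 58/115 | Chance of ≥ 69/115 |
|---|---|---|
| 50% | 50.0% | 2.0% |
| 55% | 85.9% | 16.3% |
| 60% | 98.5% | 54.0% |

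The bound controls chance passes near 50%, but it adds no comparator. The 69/115 against 86/115 example passes with the bound in place.

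**The case against.** The strongest defense is that a majority return is a pragmatic acceptability benchmark. Acceptability of self-sampling is part of the stated purpose in Section 3, and for that question a pooled rate is a reasonable summary. This stands. It is a reason to keep the threshold as a description, but not to let it decide whether the tailored toolkit succeeded.

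A second defense is that the rule sits beneath the bullet on the tailored toolkit, so the tailored group is implied. That reading is fair and it defeats the pooled example. It does not supply a comparator, as Reading B shows.

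A reader might also infer three stronger things that the documents do not support:

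- *That the trial has a 50% false-positive rate.* Criterion 1 is met half the time at a true 50% with n = 345 or 115 (47.9% with n = 350), but this is true of any point-estimate threshold set at the true rate. The documents do not present 50% as a null to be rejected and set no alpha. The rule also seldom passes well below 50%: 3.1% of the time at a true 45% pooled, and 1.5% at a true 40% in one group of 115. Overall success needs criterion 2 as well, so these are not probabilities of declaring success.
- *That the denominator might be women approached.* Section 9 introduces the evaluation with enrolled participants, and following the kit's instructions presupposes having a kit.
- *That a lower confidence limit above 50% is required.* That is a design choice with a real cost, shown in the table above.

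**Conclusion.** The point holds on both readings of criterion 1. Pooled, the criterion can be met with the tailored group about 16 points below each other group. Restricted to the tailored group, it can be met with that group about 15 points below the others. Criterion 2 and Section 12 do not guard against either case.

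The defect is the missing arm and comparator in a rule used to judge the tailored toolkit. The majority threshold is not wrong in itself. The sizes rest on illustrative return rates, and the probabilities assume independent returns, which snowball recruitment may not satisfy. The between-arm difference supports H1 only so far as the assignment of women makes the three groups comparable.

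**What to change.** In Section 9:

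1. Apply criterion 1 to women handed a culturally tailored kit. Put all of them in the denominator and count every woman who does not return a sample as not returned.
2. Keep a count, without identifiers, of kits handed out in each arm, so that destroying data on withdrawal (Section 14) does not shrink the denominator.
3. Report the return rate with an exact 95% CI for each arm.
4. State that H1's claim of improved screening rests on the between-arm difference in return rate, tailored versus untargeted message and tailored versus plain packaging, each with its 95% CI. Add this comparison to the analysis text in Section 12.
5. State that the majority threshold is a descriptive acceptability benchmark and does not support a claim for tailoring.

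A requirement that the lower 95% limit exceed 50% (69/115) is optional. If it is adopted, its loss at a true 60% (from 98.5% to 54.0%) should be stated.

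The cost is a few sentences, a running count of kits and a little more analysis. The real downside is that a claim for tailoring becomes harder to make. With 115 per arm and two-sided 0.05, power for one comparison is about 33% for 50% versus 60%, 63% for 50% versus 65% and 88% for 50% versus 70% (illustrative rates). The interval for the difference should therefore be reported whether or not it excludes zero.
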